## **PASS Information – Study SARSAC09715 – Non-Interventional PASS survey to evaluate the effectiveness of the Isatuximab Educational Materials**

Study title:	Non-Interventional Post-Authorisation Safety Study (PASS) survey to evaluate the effectiveness of the Isatuximab Educational Materials, to minimise the Risk of Interference for blood typing (minor antigen) (positive indirect Coombs' test)
Protocol edition No.:	1.4
Date of protocol edition:	21 October 2021
EU PAS register No.:	EUPAS46988
Active substance:	Isatuximab (ATC code: L01XC38)
Medicinal product:	SARCLISA
Product reference:	EMA/H/C/004977/XXXX
Procedure No.:	EMA/H/C/004977/XXXX
Marketing Authorisation Holder:	Sanofi-Aventis Groupe
Joint PASS:	No
Research question and objectives:	
The study aims to assess the effectiveness of the isatuximab Educational Materials in terms of process indicator, meaning implementation, knowledge and behaviour with respect to the safety messages conveyed in these materials.
 
Objectives:
 

1) Describe the implementation of the additional Risk Minimisation Measures (aRMMs) to the target population, the time period(s) of implementation in each participating country (starting from local regulatory approval) and materials used,

2) Assess the knowledge of the target audience about the risk and its management

3) Assess the behaviour of HCPs with respect to the safety messages

Countries of study:	5 countries confirmed for participation: France, Switzerland, Austria, Sweden, and the Netherlands. 9 countries will be included, and the other potential countries include (but are not restricted to): Germany, Finland, United Kingdom (UK), Italy, Poland and Hungary
Author:	Epidemiology and Benefit-Risk, Global Pharmacovigilance

## 2 List of Abbreviations

AE	Adverse event
aRMM	Additional risk minimisation measures
ASCT	Autologous stem cell transplant
ATC	Anatomical therapeutic chemical
CD	Cluster differentiation
DTT	Dithiothreitol
EMA	European Medicines Agency
ENCePP	European Network of Centres for Pharmacoepidemiology and Pharmacovigilance
GVP	Good pharmacovigilance practices
HCP	Healthcare professional
IAT	Indirect Antiglobulin test
MAH	Marketing Authorisation Holder
MM	Multiple myeloma
PASS	Post-authorisation safety study
PL	Package leaflet
PSUR	Periodic Safety Update Report
Q1	First quantile
Q3	Third quantile
RBC	Red blood cell
SAP	Statistical analysis plan
SmPC	Summary of Product Characteristics
WHO	World Health Organization
UK	United Kingdom

---

### 3 Responsible Parties

---

#### Study Scientific Committee

[Not Applicable](#)

---

## 4 Abstract

Title Non-Interventional PASS survey to evaluate the effectiveness of the isatuximab Educational Materials, to minimise the Risk of Interference for blood typing (minor antigen) (positive indirect Coombs' test).
Study No. SARSAC09715
Protocol Edition No. and Date 1.4, 21 October 2021
Author Epidemiology and Benefit-Risk, Global Pharmacovigilance
Rationale and Background 
Multiple myeloma (MM) is a malignant plasma cell disease that is characterised by clonal proliferation of plasma cells in the bone marrow and the production of excessive amounts of a monoclonal immunoglobulin. The estimated 5-year prevalence of multiple myeloma reported by the International Association for Research on Cancer (in 2018) is 120 391 (16.2 per 100,000).(1) MM is a disease predominantly associated with advanced age with more than 80% of patients aged 60 years or older. Patients with MM are likely to develop bone pain, bone fractures, fatigue, anaemia, infections, hypercalcaemia, and renal function impairment, because of their disease.(2)
 
The disease course for MM varies with the aggressiveness of the disease and related prognostic factors. Treatment options and survival are based on the patient's age, fitness, and disease status. Patients under the age of 65, and presenting with symptomatic active disease in good physical health, will generally receive initial therapy with autologous stem cell transplantation (ASCT).(3) To achieve cytoreduction of the disease before collecting stem cells, induction chemotherapy is administered. In the long term, however, there is currently no cure for multiple myeloma, which is characterised with frequent relapses.
 
Isatuximab is a naked monoclonal antibody targeting a cluster of differentiation (CD) 38, a cell surface antigen expressed in haematological malignancies from B-lymphocyte, T-lymphocyte and myeloid origin. Isatuximab has been investigated with various regimens, including in combination with pomalidomide and dexamethasone for the treatment of multiple myeloma in a Phase 3 randomised, open-label, multicentre study in patients with refractory or relapsed and refractory multiple myeloma (ICARIA-MM).(4)
 
The approved therapeutic indication for SARCLISA (isatuximab) is in combination with pomalidomide and dexamethasone, for the treatment of adults patients with relapsed and refractory multiple myeloma who have received at least two prior therapies including lenalidomide and a proteasome inhibitor and have demonstrated disease progression on the last therapy. On 25 February 2021, the CHMP Positive Opinion was received and on 15 April 2021, the European Commission decision was issued for the extension of indication for SARCLISA (isatuximab) in combination with carfilzomib and dexamethasone (kd) for the treatment of adult patients with relapsed multiple myeloma who have received at least one prior therapy.
 
The European Commission decision for marketing authorisation approval was obtained on 30 May 2020. Routine pharmacovigilance will be carried out to monitor the safety of SARCLISA. Additional risk minimisation activities are proposed to minimise the following important identified risk: interference for blood typing (minor antigen) (positive indirect Coombs' test). The rationale for these additional risk minimisation activities is that isatuximab binds to endogenous CD38 found at low levels on red blood cells (RBC) and may interfere with blood bank compatibility testing, including antibody screening and cross-matching. Lack of RBC phenotyping prior to starting the isatuximab treatment, could therefore result in adverse clinical outcomes for the patient due to delaying a transfusion or, in the case of urgent transfusion, there is a small risk of transfusion related haemolysis. In clinical trials, specific instructions are provided to investigational sites to have blood typed and screened performed prior to the initiation of therapy; in the pivotal clinical trial (Study EFC14335),


the proportion of patients who needed red blood cells transfusion was 30% and no RBC transfusion-related complications associated with interference for blood typing were reported.

Some countries (Australia) have established a policy for phenotype screening prior to the initiation of therapy with CD38 class agents, following the marketing approval of the first in class anti-CD38 (daratumumab) and/or methods to mitigate the risks of interference,(5) and such methods will be included in the educational materials developed for isatuximab. The extent of the compliance to this risk mitigation in clinical practice, however, is not known.

It is critical to ensure that key safety precautions conveyed in the educational materials are well understood and adhered to by prescribing healthcare professionals (HCPs) and blood banks in the real-world setting. Additional risk minimisation measures (aRMM) in the form of Educational materials will be distributed to relevant HCPs such as clinicians and blood banks professionals, as well as Patient Cards will be provided to patients via their HCPs. According to the GVP Module XVI – Risk minimisation measures: selection of tools and effectiveness indicators (Rev 2) dated 28 March 2017,(6) evaluating the effectiveness of aRMM is necessary to establish whether an intervention has been effective, and, if not, why and which corrective actions are necessary.

This study is therefore designed to evaluate the following aspects of the aRMM: the process itself (i.e. to which extent the materials have been implemented as planned) and its impact on knowledge and behavioural changes in the target audience.

### **Research Questions, Objectives and Hypotheses**

The study aims to assess the effectiveness of the isatuximab Educational Materials in terms of process indicator, meaning implementation, knowledge and behaviour with respect to the safety messages conveyed in these materials.

#### **Objectives:**

- 1) Describe the implementation of the aRMMs to the target population, the time period(s) of implementation in each participating country (starting from local regulatory approval) and materials used
- 2) Assess the knowledge of the target audience about the risk and its management
- 3) Assess the behaviour of HCPs with respect to the safety messages

#### **Hypothesis:**

We hypothesize that:

- At least 80% of the HCPs (both prescribers and non-prescribers) will provide correct responses to the first knowledge question, which is identified as the key question.

AND

- 80% of the prescribers will provide correct responses to at least five out of seven behaviour questions.

AND

- 80% of the non-prescribers will provide correct responses to at least two out of three behaviour questions.

### **Study Design**

This is a non-interventional cross-sectional study among HCPs involved in the treatment of MM with SARCLISA (isatuximab) in selected European countries.

The study is a cross-sectional survey planned to be conducted within 12 to 18 months after implementation of educational materials in each country. The surveys will be conducted online, using structured questionnaires, comprising close-ended questions where the response format is either the selection of a single response or selection of a number of responses as appropriate. Information will be collected from HCPs using the online LiveTracker™ platform. LiveTracker™ is a cloud-based, real-time, continuous electronic data collection platform tracker that delivers real-world evidence data.

This PASS will be conducted according to the Guideline on good pharmacovigilance practices (GVP) – Module VIII (Rev 3) dated 9 October 2017 2017 (7) and according to scientific standards defined in the European Network of Centres for Pharmacoepidemiology and Pharmacovigilance (ENCePP) guide on methodological standards(8)

### Population

The survey will be self-administered through electronic communication in countries selected considering the following criteria:

- Target population size (haematology/oncology centres and blood banks/transfusion centres)
- Representativeness in terms of European region
- Feasibility in terms of regulatory implementation at national level

The GVP Module XVI guidelines recommend that effectiveness of aRMMs is measured within 12 to 18 months after implementation of the material(s). As a result, data collection would start within 3 months of protocol approval (between Q3 2021 and Q2 2022). The number of countries will be defined in order to reach the overall target sample size in representative areas of Europe. Based on the estimated launch sequence that will be progressive throughout 2021 and the due date for the final report in Q3 2023, the data collection will most likely take place until at least the end of 2022 and potentially up to Q1 2023.

Countries confirmed for participation: France, Switzerland, Austria, Sweden, and the Netherlands. There will be a maximum of nine countries included in this study and the other potential countries include (but are not restricted to): Germany, Finland, United Kingdom (UK), Italy, Poland and Hungary.

HCPs who meet each of the inclusion criteria and none of the exclusion criteria are eligible to participate in this study.

### Inclusion Criteria

- The HCP is involved in the management and follow-up of multiple myeloma, such as oncology/haematology specialists and HCPs associated with blood banks/transfusion centres who have not necessarily prescribed isatuximab.
  - Prescribers (Oncologists/Haematologists): The HCP has prescribed isatuximab at least once.
  - Non-prescribers (Blood banks/transfusion centres): The HCP has provided blood products at least once for a patient treated with isatuximab.
- The HCP provides consent to participate.

### Exclusion Criteria

- The HCP has previously been enrolled in this study.

### Variables

Variables related to the following HCPs' characteristics will be collected:

- Participation (e.g. response rate)
- Practice setting
- Implementation:
  - Receipt of the educational materials
- **Knowledge** of each safety messages

Prescribers	Non-prescribers

 
1. Key safety message: Isatuximab is associated with risk of interference with blood compatibility tests.
 
2. There is currently no available information on how long the interference may persist after the last infusion of isatuximab. Based on the half-life of isatuximab, the interference with indirect antiglobulin tests may persist for approximately six months after the last infusion.
 
	
 
1. Key safety message: Isatuximab is associated with risk of interference with blood compatibility tests.
 
2. Isatuximab bound to CD38 on RBCs and may mask the detection of antibodies to minor antigens in the patient's serum. Isatuximab may interfere with routine blood compatibility tests with potential false positive reactions in Indirect Antiglobulin test (IAT).
 

	3. The determination of a patient's ABO and Rh blood type are not impacted.				

 
● Behaviour with respect to the actions listed in the educational materials:
 
					

  
 Prescribers	Non-prescribers	
   
  
 
1. All patients should be blood typed and screened prior to start treatment with isatuximab.
 
2. Consider phenotyping prior to starting isatuximab treatment as per local practice.
 
3. If treatment with isatuximab has already started, inform the blood bank that the patient is receiving isatuximab.
 
4. In the event of a planned transfusion, notify blood transfusion centres about the risk of interference with indirect antiglobulin tests.
 
5. Verify standing orders for transfusions to determine if your patient received isatuximab within the last year.
 
6. Give the Patient Card to the patients and advise them to carry it at all time and until months after the last dose of isatuximab. Provide patient's pre-isatuximab compatibility profile, if available, to the blood bank.
 
7. Ask your patient to tell their other healthcare professionals that they have received isatuximab, particularly before a transfusion, and to show them their Patient Card.
 
 	 
 
1. In case of urgent need for transfusion, non-cross matched ABO/RhD compatible RBC units can be administered as per local bank practices.
 
2. The interference mitigation methods include treating reagent RBCs with DTT to disrupt isatuximab binding or other locally validated methods.
 
3. Since the Kell Blood group system is also sensitive to DTT treatment, Kell-negative units should be supplied after ruling out or identifying alloantibodies using DTT-treated RBCs.
 
 	
  
	Prescribers	Non-prescribers	
 
1. All patients should be blood typed and screened prior to start treatment with isatuximab.
 
2. Consider phenotyping prior to starting isatuximab treatment as per local practice.
 
3. If treatment with isatuximab has already started, inform the blood bank that the patient is receiving isatuximab.
 
4. In the event of a planned transfusion, notify blood transfusion centres about the risk of interference with indirect antiglobulin tests.
 
5. Verify standing orders for transfusions to determine if your patient received isatuximab within the last year.
 
6. Give the Patient Card to the patients and advise them to carry it at all time and until months after the last dose of isatuximab. Provide patient's pre-isatuximab compatibility profile, if available, to the blood bank.
 
7. Ask your patient to tell their other healthcare professionals that they have received isatuximab, particularly before a transfusion, and to show them their Patient Card.
 
	
 
1. In case of urgent need for transfusion, non-cross matched ABO/RhD compatible RBC units can be administered as per local bank practices.
 
2. The interference mitigation methods include treating reagent RBCs with DTT to disrupt isatuximab binding or other locally validated methods.
 
3. Since the Kell Blood group system is also sensitive to DTT treatment, Kell-negative units should be supplied after ruling out or identifying alloantibodies using DTT-treated RBCs.
 
	
Prescribers	Non-prescribers				

 
1. All patients should be blood typed and screened prior to start treatment with isatuximab.
 
2. Consider phenotyping prior to starting isatuximab treatment as per local practice.
 
3. If treatment with isatuximab has already started, inform the blood bank that the patient is receiving isatuximab.
 
4. In the event of a planned transfusion, notify blood transfusion centres about the risk of interference with indirect antiglobulin tests.
 
5. Verify standing orders for transfusions to determine if your patient received isatuximab within the last year.
 
6. Give the Patient Card to the patients and advise them to carry it at all time and until months after the last dose of isatuximab. Provide patient's pre-isatuximab compatibility profile, if available, to the blood bank.
 
7. Ask your patient to tell their other healthcare professionals that they have received isatuximab, particularly before a transfusion, and to show them their Patient Card.
 
	
 
1. In case of urgent need for transfusion, non-cross matched ABO/RhD compatible RBC units can be administered as per local bank practices.
 
2. The interference mitigation methods include treating reagent RBCs with DTT to disrupt isatuximab binding or other locally validated methods.
 
3. Since the Kell Blood group system is also sensitive to DTT treatment, Kell-negative units should be supplied after ruling out or identifying alloantibodies using DTT-treated RBCs.
 
				

Data Sources
 
This study will require primary data collection, as the most appropriate method of data collection for the study objectives is through questionnaires. A set of standard questions will be developed for each target group and validated after a testing phase. The target populations will include HCPs involved in the management and follow-up of multiple myeloma, such as oncology specialists and physicians associated with transfusion centres. Multiple reminders will have to be sent in order to maximise the response rate. A small amount of incentive payment will be made to HCPs as a compensation for the time spent to complete the questionnaire (about 15 minutes).
					

Study Size
 
The proportions of interest (p) here are the proportions of HCPs knowledgeable and adherent to the aRMMs. As the proportion of interest (p) is not known at the time of this document, we may consider it to be 50% (maximum uncertainty). Such a hypothesis yields the most conservative (largest) sample size. Based on a minimum level of precision of 5%, the minimum required sample size would be 384 for precision levels of 5% within each sub-population of interest. In order to obtain this number of completed questionnaires in our study, it is estimated that approximately 6,000 to 9,000 HCPs will be approached.
 
Feasibility will be evaluated to estimate the number of HCPs to invite in order to obtain the target number of questionnaires correctly answered.
					

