HCP non-prescribers are targeted to be, at minimum, 10% to 25% of the total HCPs, meaning that the prescribers are targeted to be, at maximum, 75% to 90% of the total HCPs. Considering that the proportion of each types of HCPs may vary among countries based on the country-specific distribution of educational materials, it is acceptable that, in certain countries, the final proportion of non-prescribers may exceed 25%.

Table 3 presents the number of invitation emails to be sent and the estimated target numbers of prescribers and non-prescribers in each potential study country.

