## 9.5 Study Size

The proportions of interest (p) here are the proportions of HCPs knowledgeable and adherent to the aRMMs. As the proportion of interest (p) is not known at the time of this document, we may consider it to be 50% (maximum uncertainty). Such a hypothesis yields the most conservative (largest) sample size. Based on a minimum level of precision of 5%, the minimum required sample size would be 384 for precision levels of 5% for the overall population. The sub-populations of interest will include prescribers (75% to 90%) and non-prescribers (10% to 25%) but the study is not powered for the analysis by sub-population.

Of note, similar aRMMs were distributed to HCPs in Europe after the market authorisation was granted to the first-in-class compound (daratumumab). Based on the information published in February 2021, a total of 408 participants completed the questionnaires.

In order to obtain 400 completed questionnaires in our study, it is estimated that approximately 6,000 to 9,000 HCPs will be approached. This is based on the details provided in [section 9.2.3](#).

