**AND**

- 3 At least two out of three behaviour questions for non-prescribers.

The first knowledge question regarding the safety message “*isatuximab is associated with risk of interference with blood compatibility tests*” is defined as the key question. This knowledge question has more weight than all the other questions to assess the effectiveness of aRMM, because it provides an overarching safety message to inform both prescribing and non-prescribing HCPs about the major risk. Thus, at least 80% of the HCPs are expected to provide correct responses to this key question.

In addition, this threshold of 80% also applies to the behaviour questions—without identification of specific key questions—as part of the satisfactory criteria to assess the effectiveness of aRMM. The rationale for not identifying key questions from these behaviour questions is that prescribers and non-prescribers have different risk mitigation approaches to manage the interference and to avoid possible resulting adverse clinical consequences. Also, prioritization of questions could not be done within the behaviour questions. The pre-defined threshold for correct responses on a proportion of behaviour questions (i.e., 5/7 or 2/3) has been set to be similar between prescribers and non-prescribers.

The satisfactory threshold has been set at 80% to be in line with similar previous research.(10)

This combined approach of a satisfactory threshold of 80% on the key knowledge question and a certain proportion of behaviour questions intends to systematically assess the overall effectiveness of aRMM.

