## 9.9 Limitations of the Research Methods

All data supplied will be self-reported by the HCP, and it will not be possible to objectively verify information. The number of HCPs included will vary among countries, so the precision of country-level subgroup analyses will vary. The study uses descriptive statistics only. Therefore, it is not possible to determine whether findings are statistically significant or could be due to chance. However, given that the main objectives are to describe implementation of the aRMMs and to assess knowledge and behaviours, descriptive statistics are sufficient.

The survey will be completed by HCP on a voluntary basis. Thus, there is always the possibility that HCP accepting to participate will have different characteristics and different behaviours than non-responders. In order to identify any such selection bias, the characteristics of responders and non-responders will be described. Detailed description on minimizing selection bias during recruitment can be found in Section 9.2.

In addition, in order to reduce information bias and the possible Hawthorne effect, questions will be close-ended to avoid errors in interpreting free-texts during assessment; questions in questionnaire will not be revealed before the HCP opens it; HCPs will not have the possibility to come back and change their answers once submitted and will not be contacted to clarify or revise their survey responses. The results will reflect the knowledge, understanding and

 Non-responder's characteristics available in the LiveTracker™ panel profile.

 Overall target population characteristics available in the LiveTracker™ panel profile.

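### The abstract claims 5-point precision within each HCP type; section 9.5 and Table 3 support it only for the whole sample, and non-prescribers get about 10 to 15 points

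*Protocol*

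**What the plan says.** The abstract (section 4, Study Size) assumes a proportion of 50%, asks for a precision of 5%, and concludes that "the minimum required sample size would be 384 for precision levels of 5% within each sub-population of interest". Its Main analysis paragraph identifies the sub-population as the type of HCP, so the sentence refers to prescribers and non-prescribers separately.

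Section 9.5 uses the same inputs but says "the minimum required sample size would be 384 for precision levels of 5% for the overall population", and then that "the study is not powered for the analysis by sub-population".

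Section 9.2.3 plans about 400 HCPs and sets the split: "HCP non-prescribers are targeted to be, at minimum, 10% to 25% of the total HCPs". The Table 3 totals are 300-360 prescribers and 40-100 non-prescribers.

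Section 9.7.4 defines success through three criteria joined by AND, each requiring 80% of the relevant HCPs. They are the key knowledge question for both types, five of seven behaviour questions for prescribers, and the criterion worded "At least two out of three behaviour questions for non-prescribers".

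Section 9.9 says that only descriptive statistics are used and continues: "Therefore, it is not possible to determine whether findings are statistically significant or could be due to chance".

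**The concern.** The two study-size statements give different scopes to one number, so they cannot both be right. A reader who relies on the abstract will take the non-prescriber result to be known to within 5 points.

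This matters because of how that result is used. The third criterion rests on non-prescribers alone and, since all three must be met, it can fail the whole assessment by itself. It is also judged on the smallest group, by whether an observed percentage reaches 80%. Section 9.9 then tells the reader that the role of chance cannot be determined, although the study was sized on the half-width of an interval, which is a measure of sampling error.

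**Working it through.** **Inputs.** Proportion 50% and precision 5 points (abstract and section 9.5); about 400 HCPs (section 9.2.3); 300-360 prescribers and 40-100 non-prescribers (Table 3 totals); threshold 80% (section 9.7.4). The protocol states no confidence level. Two-sided 95% is assumed because it returns the protocol's figure.

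**Step 1: reproduce 384.** n = z² p(1-p)/d² = 1.96² × 0.25 / 0.05² = 384.2. The figure is correct as the size of one group.

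**Step 2: what the abstract's sentence would need.** Five points within each type requires 2 × 384 = 768 completed questionnaires, against about 400 planned. At the protocol's expected yield of 4.4%-6.8%, 384 non-prescribers alone would take 384/0.068 ≈ 5,600 to 384/0.044 ≈ 8,700 invitations. Table 3 plans 600-2,250 to that group.

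**Step 3: precision at the planned sizes.** Half-width = 1.96 × √(p(1-p)/n), in percentage points. For example, n=40 and p=50% gives 1.96 × √(0.25/40) = 15.5.

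| Group | n | p = 50% | p = 80% |
|---|---|---|---|
| Overall | 400 | 4.9 | 3.9 |
| Prescribers | 360 | 5.2 | 4.1 |
| Prescribers | 300 | 5.7 | 4.5 |
| Non-prescribers | 100 | 9.8 | 7.8 |
| Non-prescribers | 40 | 15.5 | 12.4 |

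Exact (Clopper-Pearson) intervals at 50% are slightly wider for non-prescribers: half-widths of 10.2 points at n=100 and 16.2 at n=40.

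**Step 4: consequence for the third criterion.** At n=40 one respondent is 1/40 = 2.5 points, so 32/40 (80%) meets the threshold and 31/40 (77.5%) does not. The exact 95% interval is 64%-91% for 32/40 and 71%-87% for 80/100. Binomial probabilities for the criterion:

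| True non-prescriber rate | Outcome | n=40 | n=100 |
|---|---|---|---|
| 75% | met | 30% | 15% |
| 85% | missed | 14% | 7% |

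**The case against.** The strongest reply is that this is a slip in the abstract with no operational effect. The number 384 is right, the abstract's next sentence itself treats it as the study total, and recruitment follows section 9.5. That stands: nothing here shows the study to be mis-sized, and a reader who infers that it must grow to 768 goes beyond the documents, because section 9.5 claims precision for the whole sample only. The abstract sentence is still false as written.

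A reader might also infer that the protocol conceals the uncertainty or will report no intervals. Neither is supported. Section 9.5 disclaims power by sub-population, section 9.9 warns about chance and about varying country-level precision, and section 9.7.1 defers detail to a separate SAP that is not available here and may include intervals. The SAP could not, however, correct the abstract.

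A third tempting reading is that non-prescriber precision is three times worse than stated. That holds only at n=40 and p=50% (15.5/5 = 3.1). At n=100 the ratio is 2.0, and at p=80% it is 1.6-2.5. The non-prescriber share is also given as a minimum and may exceed 25% in some countries. For prescribers at 80%, 4.1-4.5 points is inside the promised 5.

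Finally, the section 9.9 caution has value. With a 4.4%-6.8% expected final response and voluntary participation, a binomial interval covers only part of the uncertainty. This argues for rewording the sentence, not deleting it.

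**Conclusion.** The point holds as a misstatement of precision. The abstract contradicts section 9.5, and its version is not delivered by the planned sample. At p=50% prescribers miss 5 points narrowly (5.2-5.7) and non-prescribers miss it by a factor of two to three (9.8-15.5). At p=80% only non-prescribers miss it (7.8-12.4). The consequence is concentrated in the third criterion, which that group alone decides and which one respondent can turn at the lower end of the planned range.

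The section 9.9 sentence is too absolute: an interval for a proportion needs neither a comparator nor a test. The conclusion assumes 95% confidence, simple binomial sampling and the Table 3 totals. It does not extend to the 384 itself, the 80% threshold or the planned total, none of which is shown to be wrong.

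**What to change.** - **Abstract, Study Size:** replace the sentence with the section 9.5 statement. Add the approximate 95% half-widths at p=50%: 4.9 points overall at n=400, 5.2-5.7 for prescribers, 9.8-15.5 for non-prescribers. State the confidence level.
- **Section 9.7.4:** keep the 80% point-estimate threshold unchanged and report an exact 95% confidence interval beside each of the three criteria. Do not add an inconclusive category for intervals that include 80%. That would replace the protocol's rule: a clear pass among non-prescribers would need 38/40 or 89/100, and at a true rate of 85% there would be no verdict 95% (n=40) or 84% (n=100) of the time.
- **Section 9.9:** reword the sentence on chance to say that no hypothesis tests are planned, that the intervals express sampling error only, and that they do not cover non-response or self-selection.

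The cost is protocol wording and three intervals. The sample size, questionnaire and success rule do not change. The downside is that the stated precision for non-prescribers becomes visibly less favourable.
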